4.5 Safety Evaluation

Safety analysis will be carried out for the safety analysis set, to include all patients who receive at least one dose of study drug. Patients who do not complete the study, for whatever reason, will have all available data up until the time of termination included in the analysis.

4.5.1 Exposure to Study Treatment

Extent of exposure to both study treatments will be summarized for the safety analysis set by study phase and cohort. The duration of exposure to each treatment will be presented in days and calculated as the date of last dose of study drug minus the date of

first dose of study drug, plus one. Duration of exposure, number of patients treated (by duration), and total dose received (mg) will be summarized using descriptive statistics.

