3.16. Restarting Study Drugs at Relapse

Patients who experienced clinical benefit while on study treatment, and then experience progressive disease while not receiving VRx-3996/valganciclovir, may have study drugs restarted if the following conditions are met:

- Restarting study drugs is considered in the patient's best interest by the Investigator
- The patient has not developed any contraindications to either study drug
- The Investigator has discussed restarting study drugs with the study Medical Monitor who agrees that restarting of study drugs is appropriate
- The study has not been closed by the Sponsor

Patients will generally restart study drugs at the RP2D; however, the dose and schedule may be altered if considered in the best interest of the patient by the Investigator, Medical Monitor, and Sponsor representative.

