5.1.8. Dose Adjustments/Modifications/Delays

Given the expectation that both study drugs are required for activity, both agents will be held and restarted in parallel unless toxicity is clearly associated with VRx-3996 and there is clinical justification to continue dosing with valganciclovir alone. For non-hematologic toxicity requiring dose modification see [Table 12](#).

Table 12: Requirements for Dose Hold Secondary to Non-Hematologic Toxicity

Toxicity (CTCAE)	Requirement for Dose Hold
Grade 1 or 2	No dose hold required
Grade 3+	Hold subsequent dosing until toxicity has resolved to at least Grade 1 or baseline

In the event that any of the following hematologic AEs are observed on study, the dose of VRx-3996 and valganciclovir will be held:

- ANC <500 cells/ μ L
- PLT count <35,000/ μ L
- Hemoglobin (HGB) is <8 g/dL

If a hold is implemented for study drug-related toxicity, patients may restart study drugs only if the following conditions are met or if agreed with the Medical Monitor:

- The AE has resolved to at least Grade 1 or baseline for non-hematologic AEs and Grade ≤ 2 hematologic toxicity related to study drug
- The AE is not expected to recur in the opinion of the Investigator with subsequent study drug administration based on an intervention such as prophylactic use of appropriate treatment (e.g., prophylactic anti-emetics), or a reduction in the dose of one or both of the study drugs
- Continued administration of study drugs is considered to be in the patient's best interest based on the opinion of the study Investigator

Patients should be followed up approximately twice weekly for resolution of the toxicity. Study days will continue to accrue during dose holds and other scheduled procedures as per [Table 15](#) should not be delayed. If the dose is held for more than 14 days, the Investigator should consult with the Medical Monitor before dosing resumes.

If a patient has multiple dose interruptions for study drug toxicity or has had to interrupt for more than 14 days, a dose reduction should be considered. Dose reduction for VRx-3996 will be in 10 mg increments and for valganciclovir from 900 mg to 450 mg. Re-escalation of study drug dose may only be performed after approval by Medical Monitor.

There are additional criteria for modification of the valganciclovir dose based on renal function as outlined in [Section 5.2.3](#).

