5.5. Assessment of Study Drug Compliance

Patient compliance with study drugs will be assessed during study participation. The specific method used to assess study drug compliance may include paper diaries or an automated phone-based system to collect study drugs capsule/tablet counts. Details on the specific method used will be included in the Study Manual.

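### Duration of exposure is defined as a first-to-last-dose span, so dose holds and possibly the whole gap before a permitted restart count as time on drug, and no planned-dose denominator is set.

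*SAP*

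**What the plan says.** SAP 4.5.1 (Exposure to Study Treatment) gives duration of exposure to each drug, in days, as "calculated as the date of last dose of study drug minus the date of" "first dose of study drug, plus one". It also plans a count of patients treated by duration, and states that "total dose received (mg) will be summarized using descriptive statistics". It has no rule for holds or for a second course of treatment, and it compares dose received with no planned dose.

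The protocol provides for both situations:

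- **Holds.** Protocol 5.1.8 says "Study days will continue to accrue during dose holds". The sentence beginning "If the dose is held for more than 14 days" requires a consultation before dosing resumes but sets no upper limit on the hold.
- **Restart.** Protocol 3.16 says "Patients who experienced clinical benefit while on study treatment, and then experience progressive disease while not receiving VRx-3996/valganciclovir, may have study drugs restarted", subject to conditions, none of which limits the length of the gap. Protocol 3.1.2 has a similar provision.
- **Adherence.** Protocol 5.5 says "Patient compliance with study drugs will be assessed during study participation", by diary or by phone-based capsule and tablet counts. The Schedule of Events (Table 15) marks the assessment at every treatment-visit column. The SAP plans no summary of compliance.

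**The concern.** Safety and tolerability is the first-listed primary objective in both documents. An exposure table should tell the reader how long patients were actually on each drug and how much of the assigned regimen they received.

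A first-to-last-dose span answers neither question once dosing is interrupted. A patient who stops, relapses off drug and restarts may be shown as continuously exposed. A patient held for weeks has the same duration as one who was never held. Total mg moves in the right direction, but without a planned amount beside it a reader cannot tell a short full-dose course from a long, poorly delivered one. Both effects make time on drug look longer than it was, and the inflated figure also feeds the count of patients by duration.

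**Working it through.** The plan states no figure to reproduce, so the SAP rule was applied to day-by-day dosing calendars.

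**Inputs from the documents.** The duration rule is from SAP 4.5.1. The Phase 2 schedule is from Protocol 3.2.4: nanatinostat (VRx-3996) 20 mg once daily, 4 days on and 3 off, and valganciclovir 900 mg once daily. The cycle is 28 days. Nanatinostat per full cycle is 4 days × 4 weeks = 16 doses, and 16 × 20 mg = 320 mg.

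**Assumed inputs.** Hold and gap lengths are assumptions, because the documents give neither frequencies nor typical lengths.

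**Step 1: holds within four cycles (112 days).**

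| Hold | Valganciclovir: SAP duration | Valganciclovir: hold removed | Ratio | Nanatinostat: SAP duration | Nanatinostat: total dose |
|---|---|---|---|---|---|
| none | 112 days | 112 days | 1.00 | 109 days | 64 × 20 = 1,280 mg |
| 14 days | 112 days | 112 − 14 = 98 days | 112/98 = 1.14 | 109 days | 56 × 20 = 1,120 mg |
| 21 days | 112 days | 112 − 21 = 91 days | 112/91 = 1.23 | 109 days | 52 × 20 = 1,040 mg |

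Duration does not react to the hold. Total dose does, provided it is built from actual intake. Nanatinostat shows 109 days rather than 112 because its last dose falls before the final 3-day break. Those planned breaks are not counted as an error here: Protocol Table 5, where it sets out this schedule, says the dosing holiday is not a hold.

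**Step 2: restart.** Take four cycles, a gap, then two cycles, with the last dose read as the last dose after restart. Treated time is 112 + 56 = 168 days (valganciclovir).

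| Gap | SAP duration | Ratio to treated time |
|---|---|---|
| 84 days | 168 + 84 = 252 days | 252/168 = 1.5 |
| 168 days | 168 + 168 = 336 days | 336/168 = 2.0 |
| 336 days | 168 + 336 = 504 days | 504/168 = 3.0 |

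**Step 3: can total mg make good the loss?** Compare two patients on nanatinostat.

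- Patient A has six full cycles around a 168-day gap: 6 × 320 = 1,920 mg over about 336 days.
- Patient B has twelve cycles at half delivery: 12 × 320 × 0.5 = 1,920 mg over 12 × 28 = 336 days.

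Both planned exposure figures are practically the same for A and B, although A received the full regimen while on treatment and B received half of it.

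**Step 4: is the planned dose constant within a cohort?** SAP 4.9 records that Cohort 1 valganciclovir was 900 mg twice daily for the first 4 patients and 450 mg twice daily for the last 3. With full delivery, one cycle is 2 × 900 × 28 = 50,400 mg for the former and 2 × 450 × 28 = 25,200 mg for the latter. A cohort summary of total mg therefore mixes a twofold difference in planned dose with any real difference in delivery. Planned dose can also vary between and within patients through individual escalation (Protocol 3.1.8), reductions (5.1.8), and lower starting doses or renal adjustment (5.2.3).

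**The case against.** The strongest reply is that last minus first plus one is a common and plainly stated calendar convention, and that little rests on it. Adverse events are summarised as patient incidences, with no exposure-adjusted rates. SAP 4.1.1 and 4.6.5.5 describe the study as exploratory, with no hypothesis testing. SAP 4.5.2 tabulates events leading to interruption, reduction or discontinuation, SAP 4.5.3 lists them, and a hold of more than 7 consecutive days is itself a dose-limiting toxicity criterion in Phase 1b. All of this stands, and it limits the weight of the point.

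It also rules out three stronger readings that a reader might infer:

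- **That the adherence data go unused, or that no figure shows how much drug a patient took.** Total dose received is summarised, and its source is not named, so the counts may feed it. SAP 4.1.1 says that collected data will in general be listed by patient. What is absent is a ratio to planned dose or a compliance summary.
- **That the choice of recommended Phase 2 dose is compromised.** The Safety Review Committee sets it at the end of Phase 1b from all available safety and efficacy data (Protocol 12.3.2), and both documents already state the regimen. This table does not enter that decision.
- **That exposure will be overstated severalfold.** That would need long gaps and the post-restart reading of last dose. The documents settle neither. Restart also requires earlier clinical benefit, so a gap need not reflect intolerance.

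The remainder survives. Incidence tables show who was interrupted, not for how long or how much planned drug was lost, and Step 3 shows that the two planned exposure measures cannot supply this together.

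**Conclusion.** The point holds in a limited form. Read literally, SAP 4.5.1 counts hold days as exposure. It counts the off-treatment gap too if a restarted course supplies the last dose, and its silence on that is itself a gap. No planned-dose denominator, dose intensity, compliance rate or interruption-adjusted duration is planned, although planned dose differs even within Cohort 1.

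Under the assumed lengths the overstatement is 14% to 23% for a single hold of 14 to 21 days in four cycles, and 1.5-fold to 3-fold for a restarted patient. These are per-patient illustrations. The effect on a cohort summary depends on how many patients are held or restarted, which is not given. The consequence is confined to descriptive exposure and tolerability tables, but these serve a primary objective, so the change is worth making before database lock.

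**What to change.** Amend SAP 4.5.1 as follows.

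1. Label the existing figure as calendar duration including holds. Compute duration per treatment course and sum the courses, so that the gap before a restart is excluded. Report restarts separately.
2. Report days held, not counting the scheduled 3-day nanatinostat break as a hold.
3. Report relative dose intensity for each drug by phase and cohort: actual mg divided by planned mg on each patient's assigned schedule (once or twice daily as assigned, 4 days on and 3 off where that applies). State whether the denominator is the initially assigned dose or the dose after committee or renal adjustment. Count cycles wholly held within a course in the denominator. Name the data source for actual mg.

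The cost is SAP text and some programming, with no new visits or tests, assuming that dosing dates and capsule or tablet counts are in the database. Protocol 5.5 leaves the compliance method to the Study Manual, so this should be confirmed first. Reported exposure may come out slightly shorter.

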4.5.2 Adverse Events

Treatment-emergent adverse events (TEAEs) are defined as those adverse events (AEs) with onset after the first dose of study drug or pre-existing events that worsened by at least one grade after the first dose during the study. Treatment-emergent AEs will be summarized by study phase and cohort. Events reported with a partial onset date (e.g., month and year are reported but the day is missing) will be considered to be treatment-emergent if it cannot be confirmed that the event onset was prior to the first dose of study drug based on the available date entries.

Verbatim terms on case report forms will be mapped to preferred terms and system organ classes using the Medical Dictionary for Regulatory Activities (MedDRA, version 25.0). As an additional safety analysis, certain hematological AEs will be programmatically re-mapped to preferred terms and system organ classes consistent with CTCAE v5.0 categories. Select AE summaries will be repeated using this alternative mapping.

Summaries that are displayed by system organ class and preferred terms will be ordered by descending incidence of system organ class and preferred term within each system organ class. Summaries displayed by preferred term only will be ordered by descending incidence of preferred term. Summaries of the following types will be presented:

- Overall summary of number of unique TEAEs and patient incidence of TEAEs meeting various criteria.
- Overall summary of number of unique SAEs and patient incidence of SAEs meeting various criteria
- Patient incidence of TEAEs by MedDRA system organ class and preferred term
- Patient incidence of TEAEs by CTCAE toxicity grade, MedDRA system organ class, and preferred term.
- Patient incidence of dose-limiting toxicity AEs by MedDRA system organ class and preferred term.
- Patient incidence of TEAEs leading to dose interruption, reduction or discontinuation of valganciclovir by MedDRA system organ class and preferred term.
- Patient incidence of TEAEs leading to reduction or interruption of nanatinostat and valganciclovir by system organ class and preferred term
- Patient incidence of TEAEs leading to discontinuation of nanatinostat and valganciclovir by system organ class and preferred term

- Patient incidence of SAEs by MedDRA system organ class and preferred term.
- Patient incidence of SAEs by CTCAE toxicity grade, MedDRA system organ class, and preferred term.
- Patient incidence of TEAEs leading to study withdrawal by MedDRA system organ class and preferred term;
- Patient incidence of TEAEs leading to death by MedDRA system organ class and preferred term

Select AE summaries will also be repeated for different age subgroups (<65 years old, ≥65 years old, ≥65 years old and <75 years old, and ≥75 years old).

At each level of summarization (e.g., any AE, system organ class, and preferred term), patients experiencing more than one TEAE will be counted only once. In the summary of TEAEs by CTCAE grade, patients will be counted once at the highest severity reported at each level of summarization; in the summary of TEAEs by relationship, patients will be counted once at the closest relationship to study drug. Related events include those reported as “Possibly Related” or “Definitely Related” to study drug; events considered not related are those reported as “Unrelated” to study drug.

Adverse event data will be presented in data listings by study part, patient, cohort, and event. Serious AEs and AEs leading to discontinuation of the study drugs will be also be presented in separate data listings.

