1.12. Potential Risks and Benefits

1.12.1. Potential Risks

Both VRx-3996 and valganciclovir exhibit overlapping toxicities (i.e., thrombocytopenia and renal dysfunction) that may be increased in rate or severity with this combination.

In addition, in prior clinical studies other toxicities reported for one or both agents include fatigue, atrial fibrillation, nausea/vomiting, anemia, leukopenia, and neutropenia.

While not all have been reported for VRx-3996, toxicities reported for other HDAC inhibitors include, thrombocytopenia, neutropenia, anemia, fatigue and diarrhea.²¹

As with any new combination, toxicities, which have not been seen with either agent alone or with combinations of similar agents, may become manifest. Similar combinations (arginine butyrate combined with ganciclovir)¹⁴ have resulted in rapid tumor destruction and loss of tissue integrity resulting in death.

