12.3. Analysis of the Primary Endpoints

12.3.1. Safety Profile

The safety dataset will be used for all the safety summaries.

The incidence of all AEs will be tabulated by dose received. These AEs will be classified by System Organ Class and preferred term using the Medical Dictionary for Regulatory Activities (MedDRA).

For incidence reporting, if a patient reported more than 1 AE that was coded to the same System Organ Class or Preferred Term, the patient will be counted only once at the highest observed grade for that specific system organ class or preferred term.

An overview of AEs, which includes patient incidence of AEs, AEs by severity, SAEs, deaths, and AEs leading to discontinuation, will be presented.

A summary of the number DLTs per cohort will be provided.

Serious adverse events will be listed and summarized in a similar manner to AEs.

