1. INTRODUCTION

The purpose of this Statistical Analysis Plan (SAP) is to provide comprehensive and detailed descriptions of the methods and presentation of data analyses proposed for Viracta Therapeutics, Inc. Protocol VT3996-201 (A Phase 1b/2 Open-Label, Dose Escalation and Expansion Study of Orally Administered VRx-3996 and Valanciclovir in Subjects with Epstein-Barr Virus-Associated Lymphoid Malignancies). Descriptions of planned analyses for the clinical study report (CSR) are provided in order to avoid post hoc decisions that may affect the interpretation of the statistical analysis. Both the statistical methods applied to the study design and the planned analyses for this study are consistent with the International Council for Harmonisation (ICH) guideline *Statistical Principles for Clinical Trials (E9)* (1998). The final study analysis will be performed when the last patient with a partial response (PR) or complete response (CR) is followed for 12 months, and all enrolled subjects have completed efficacy, safety and other assessments.

This SAP will be finalized prior to data analysis and before database lock to provide comprehensive details of the tables, figures, and listings to be presented in the CSR. Any changes between the statistical methods provided in the clinical study protocol and this SAP will be explained herein; any changes or deviations from this SAP relative to the final analysis will be fully documented in the CSR. Minor changes or deviations from the templates for tables, figures, and listings need not be documented in the CSR.

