3.1.1 Phase 1b (Dose Escalation)

During the dose escalation portion of the study, dosing will be based on assigned cohort. Approximately 25 patients are expected to enroll in this phase. Cohort size will be up to 7 patients using a conventional modified 3+3 design for dose escalation studies in oncology.

On Cycle 1 Day 1, in an effort to ensure that patients tolerate oral valganciclovir prior to receiving nanatinostat, valganciclovir will be taken first, followed by nanatinostat approximately 1 hour later. For all subsequent administrations, the sequence of nanatinostat and valganciclovir can be dictated by patient convenience (e.g., both drugs may be taken together if tolerated by the patient). With the implementation of Protocol Amendment 4.0, nanatinostat and valganciclovir will be taken together at all timepoints, including Cycle 1 Day 1.

The first cycle is defined as the dose-limiting toxicity (DLT) assessment period. Grading of DLTs will be according to the National Cancer Institute Common Terminology Criteria for Adverse Events (NCI CTCAE) version 5 and detailed in Section 3.1.5 of the protocol as well as [Section 3.4.1](#) of the SAP. Patients who are unable to complete the DLT assessment period for reasons other than study drug-related toxicity may be replaced if needed to achieve at least 3 patients evaluable for DLTs.

A Safety Review Committee (SRC) comprised of study investigators, the study medical monitor and a Sponsor representative will govern the conduct of the study, and will have the option of defining additional cohorts and doses either below, above, or intermediate to the planned doses as needed based on data generated from prior cohorts. The SRC may also modify the dosing schedule for either nanatinostat or valganciclovir as required to accommodate different dosage strengths and patient convenience. However, when the schedule is adjusted, the total daily dose will remain unchanged. The Phase 1b planned doses for each cohort are provided in Table 2.

Table 2 Phase 1b Dose Levels by Cohort

Cohort Number	Dose Nanatinostat	Dose Valganciclovir
1	10 mg BID (20 mg daily dose)	900 mg BID
2a	5 mg BID (10 mg daily dose)	450 mg BID
2b	10 mg QD (10 mg daily dose)	450 mg BID

Cohort Number	Dose Nanatinostat	Dose Valganciclovir
2c	10 mg QD (10 mg daily dose)	900 mg QD
3	20 mg QD (20 mg daily dose), 4 days on and 3 days off in a 7-day regimen	900 mg QD

BID, twice daily; QD, once daily.

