4.1.1 Reporting Conventions

Tables and figures will be summarized by cohort and study phase. Tables will also include a column for all patients who receive the capsule formulation. In general, all data collected, and any derived data will be presented in patient data listings, for all enrolled patients. Listings will be ordered by site, study phase, patient number, cohort,

and assessment or event date. The cohort presented in listings will be based on the planned assignment, unless otherwise noted.

Summaries will be based on patient data from both the dose escalation and dose expansion phases up until the time when the final dose escalation patient has completed at least 12 months of follow-up from their first disease response assessment after two cycles of therapy, or until all patients have discontinued the study, died, withdrawn consent, discontinued, or are lost to follow-up, whichever occurs first.

In general, continuous variables will be summarized to indicate the study population sample size (N), number of patients with available data (n), mean, SD, median, minimum, and maximum values. Categorical variables will be summarized by the population size (N), number of patients with available data (n), number of patients in each category, and the percentage of patients in each category. Unless otherwise noted, the denominator to determine the percentage of patients in each category will be based on the number of patients with available data. Select ordinal data may be summarized using both descriptive statistics and counts and percentages of patients in each category, as appropriate.

Non-zero percentages will be rounded to one decimal place. Rounding conventions for presentation of summary statistics will be based on the precision of the variable of summarization, as it is collected in its rawest form (i.e., on the electronic case report form [eCRF] or as provided within an external file) and are outlined as follows:

- The mean and median will be rounded to one more decimal place than the precision of the variable of summarization.
- Measures of variability (e.g., SD, SE) will be rounded to two more decimal places than the precision of the variable of summarization.
- Minimum and maximum values will be presented using the same precision as the variable of summarization.

Other statistics (e.g., CIs) will be presented using the same general rules outlined above or assessed for the most appropriate presentation based on the underlying data.

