4.9 Changes in the Conduct of the Study or Planned Analyses

The following changes to planned analyses identified within the development of this SAP, relative to the descriptions provided within the clinical study protocol are listed below:

- Section 3.1.3 of the protocol includes a table for intended Phase 1b Cohort Doses.
 - The original intended Valganciclovir dose for Cohort 1 was 900 mg BID, but this was modified per the SRC recommendation after the first

4 patients. The actual Valganciclovir dosing was 900 mg BID for the first 4 patients and then 450 mg BID for the last 3 patients.

- The original intended Nanatinostat dose for Cohort 3 was 20 mg QD. The SRC later recommended to revise this dose to 20 mg QD 4 days per week following review of Cohort 1 safety data.
- Section 3.8 of the protocol states that a central review of patient scans will be performed and may include an assessment based on both Lugano and RECIL criteria. This central review was not performed.
- Section 6.4.1 of the protocol describes urine PK sample collection and, but this was not collected and will not be analyzed.

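### The protocol tabulates AEs by dose received but the SAP tabulates them by cohort without listing the change, so Cohort 1 pools two valganciclovir doses in one column

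*SAP*

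**What the plan says.** Protocol 12.3.1 (Safety Profile) states "The incidence of all AEs will be tabulated by dose received". A few lines later in the same section it asks for something laid out differently: "A summary of the number DLTs per cohort will be provided".

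SAP 4.5.2 states "Treatment-emergent AEs will be summarized by study phase and cohort". SAP 4.1.1 sets the same cohort-and-phase layout for tables and figures generally, and adds one column for all patients on capsules. SAP 4.5.1 also summarises exposure, including total dose received in mg, by study phase and cohort.

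On changes from the protocol, SAP 1 says "Any changes between the statistical methods provided in the clinical study protocol and this SAP will be explained herein". SAP 4.9 has four entries: the Cohort 1 valganciclovir change, the Cohort 3 schedule change, the central scan review that was not done, and the urine PK samples that were not collected. The basis of the AE tables is not among them.

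On Cohort 1, SAP 4.9 reports: "The actual Valganciclovir dosing was 900 mg BID for the first 4 patients and then 450 mg BID for the last 3 patients". SAP 3.1.1 says "The Phase 1b planned doses for each cohort are provided in Table 2", and that table has a single Cohort 1 row with valganciclovir 900 mg BID.

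**The concern.** The protocol uses cohort for DLT counts and dose received for AE incidence, within one short section. Protocol 12.2 also uses cohort and study phase for continuous variables and response rates, so that wording was available and was not chosen for AEs. Replacing dose with cohort is therefore a change of layout, and SAP 4.9 does not record it.

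It matters where cohort and dose are known to differ. Safety and tolerability is a primary objective, and Protocol 1.12.1 warns: "Both VRx-3996 and valganciclovir exhibit overlapping toxicities (i.e., thrombocytopenia and renal dysfunction) that may be increased in rate or severity with this combination". The first 4 patients of Cohort 1 are the only group in the Phase 1b plan on valganciclovir 1800 mg/day. SAP 4.9 also says that Cohort 3 moved to dosing on 4 days a week after review of Cohort 1 safety data, and that schedule became the Phase 2 regimen. A reader will want to know whether Cohort 1 events arose at the full or the halved valganciclovir dose. A single column cannot show this.

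**Working it through.** **Do the two documents specify the same table?**

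- Protocol 12.3.1: AE incidence by dose received; DLTs per cohort.
- SAP 4.5.2 and 4.1.1: TEAEs by study phase and cohort.
- SAP 4.5: no safety summary is described as being by dose received.
- SAP 4.9: no entry on this.

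They agree only where cohort fixes the dose.

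**Does cohort fix the dose?** Valganciclovir per day, from SAP Table 2 and SAP 4.9:

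- Cohort 1, first 4 patients: 900 × 2 = 1800 mg
- Cohort 1, last 3 patients: 450 × 2 = 900 mg
- Cohorts 2a and 2b: 450 × 2 = 900 mg
- Cohorts 2c and 3: 900 × 1 = 900 mg

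Within Cohort 1 the ratio is 1800/900 = 2, so the last 3 patients took 50% less per day. The column holds 4 + 3 = 7 patients: 4/7 = 57.1% at 1800 mg/day and 3/7 = 42.9% at 900 mg/day. On valganciclovir alone, the last 3 match the other cohorts' daily dose and not their own cohort's label.

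SAP 4.9 does not restate the VRx-3996 (nanatinostat) dose of those 3 patients. If it stayed at 10 mg BID, their combination is not a row of Table 2, so no other column could hold them.

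**What could pooling do to a reported rate?** The documents give no AE counts, so these counts are assumed. Exact (Clopper-Pearson) 95% intervals are in brackets.

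| Assumed events (900 mg BID; 450 mg BID) | 900 mg BID, n=4 | 450 mg BID, n=3 | Pooled, n=7 |
|---|---|---|---|
| 2; 1 | 50% (6.8–93.2) | 33.3% (0.8–90.6) | 42.9% (9.9–81.6) |
| 2; 0 | 50% (6.8–93.2) | 0% (0–70.8) | 28.6% (3.7–71.0) |
| 3; 0 | 75% (19.4–99.4) | 0% (0–70.8) | 42.9% (9.9–81.6) |
| 4; 0 | 100% (39.8–100) | 0% (0–70.8) | 57.1% (18.4–90.1) |

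The first and third rows give the same pooled figure from quite different patterns. The wide intervals show equally that the split describes and does not test anything.

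**The case against.** The strongest reply is that no method has changed. Phase 1b dosing is by assigned cohort and Protocol Table 5 defines each cohort by its dose, so dose received may simply mean the dose-level column. That is a fair reading for the other cohorts. It fails for Cohort 1, where the SAP itself records two doses under one label.

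Second, the split is disclosed. SAP 4.9 gives both doses, the numbers and the SRC's role, and Table 2 is introduced as planned doses. This stands. A reader might infer that the plan conceals the 4 patients at the higher dose; SAP 4.9 rules that out. What is missing is the step from that disclosure to the AE tables.

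Third, the table shells are not in the documents, so a footnote or split column may exist. This stands as a limit: pooling is inferred from SAP 4.1.1, 4.5.2, 4.9 and Table 2.

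Fourth, the information is recoverable. In part: listings allow manual tracing by patient, but SAP 4.1.1 says "The cohort presented in listings will be based on the planned assignment, unless otherwise noted", and the exposure summaries are by cohort too.

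Fifth, little depends on the column. The study is descriptive, Cohort 1's regimen is not the RP2D, and the SRC sets the RP2D from all available safety and efficacy data. This keeps the stakes modest, but it does not make the column a correct summary by dose.

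**Conclusion.** The point holds, with its known effect limited to Cohort 1. The SAP departs from the protocol's stated basis for AE incidence without listing the departure. As written, it puts 4 patients on valganciclovir 1800 mg/day and 3 on 900 mg/day in one column, so 43% of that column took half the labelled dose.

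This rests on three assumptions: that the tables follow the SAP text, that all 7 patients are in the safety set, and that the dosing in SAP 4.9 is the dose to tabulate by.

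Three stronger readings are not supported:

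- A reader might infer that many patients are misplaced, because the protocol permits escalation (3.1.8), restart at the RP2D (3.1.2, 3.16), dose reduction (5.1.8), renal adjustment (5.2.3) and a mid-study RP2D change (3.2.2). The documents do not say how many patients took these routes, and the number may be zero.
- A reader might infer that each event must be assigned to the dose at onset. The protocol does not ask for this, and assigned dose group is a legitimate basis.
- A reader might infer that the DLT summary is wrong too. Reporting DLTs per cohort is what the protocol specifies.

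**What to change.** In SAP 4.5.2, keep the cohort tables and show Cohort 1 TEAEs in two sub-columns by valganciclovir dose received: 900 mg BID (n=4) and 450 mg BID (n=3). Do the same for exposure in SAP 4.5.1, and give the VRx-3996 dose of the 3 later patients in the column label. In SAP 4.9, state that AE tables are by study phase and cohort, with this split, in place of the protocol's tabulation by dose received.

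The cost is two sub-columns and a few sentences. The dosing data are already needed for the exposure summaries. The drawback is that columns of 4 and 3 patients support description only, and a note to that effect should accompany the table. A further table attributing events to the dose at onset is optional: it would place some patients in more than one column, so the columns would no longer add up to the number of patients.
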